3.4 Demographic and Baseline characteristics

All demographic and Baseline characteristics (including the Pain Catastrophizing Scale total score) will be listed by treatment group, and subject for the randomised population. The Pain Catastrophizing Scale total score is calculated as the sum of the 13 items, ranging from 0 to 52.

Summary statistics will be provided for demographic and Baseline characteristics, by DB treatment group, for the Randomized, and mITT populations.

Q-tip test results will be listed for all screened subjects.

No statistical comparison of the treatment groups will be provided.

3.5 Medical and surgical history

Medical and surgical history, non-drug therapies and surgical procedures will be coded using the latest version of MedDRA at the time of the database lock.

Listings will present the primary system organ class, preferred term and verbatim text. The listings will be sorted by DB treatment group, subject, primary system organ class, preferred term and verbatim text.

A frequency table of the number and percentage of subjects will be provided for all medical and surgical history by primary system organ class and preferred term. The table will be presented by DB treatment group for the randomised population.

3.6 Prior and concomitant therapies

Prior and concomitant therapies will be coded using WHO-Drug Dictionary, the latest version at the time of database lock. The therapeutic class will correspond to the second level of ATC code.

Medication, non-drug therapies, physiotherapies, sex therapies and surgical procedures start and stop dates will be compared to the date of the first IMP administration to allow classification as either Prior (P) only or Concomitant (PC, C):

Prior (P)	Start and stop dates prior to the date of the first IMP administration.
Prior and Concomitant (PC)	Start date before the date of the first IMP administration and stop date on or after the date of the first IMP administration.
Concomitant (C)	Start date on or after the date of first IMP administration.

Summary tables on prior medications/non-drug therapies/surgical procedures will include “P” only, summary tables on concomitant medications/non-drug therapies/surgical procedures will include “C” and “PC”.

A treatment will be considered concomitant to a cycle if the start date was on or before the IMP administration for the cycle and the stop date was on or after the IMP administration for the cycle. A treatment can be concomitant under more than one treatment cycle, but it will be considered as concomitant only once in the overall period.

The following summaries will be provided:

- number and percentage of subjects with prior medication (category P) by ATC class and Preferred Name (PN, ATC level 2),
- number and percentage of subjects with concomitant medication (categories PC, C) by ATC class and PN (ATC level 2),
- number and percentage of subjects with prior non-drug therapy (category P) by SOC and PT,
- number and percentage of subjects with concomitant non-drug therapy (categories PC, C) by SOC and PT,
- number and percentage of subjects with prior pelvic floor physical therapy (category P) by SOC and PT,
- number and percentage of subjects with concomitant pelvic floor physical therapy (PC, C) by SOC and PT,
- number and percentage of subjects with prior sex therapy (category P) by SOC and PT,
- number and percentage of subjects with concomitant sex therapy (categories PC, C) by SOC and PT,
- number and percentage of subjects with concomitant surgical procedures by primary SOC and PT.

All these tables will be presented during the DB period by DB treatment group for the randomized population. In addition, tables related to concomitant medications/therapies/ surgical procedures will be presented during Active Treatment period all doses combined by Active Treatment Cycle and overall, for the Active Treatment population.

Listings will be provided for all the summaries listed above with the therapeutic class, preferred term/name and verbatim text. The level of concomitance will also be presented (P, PC, C).

A listing of prohibited concomitant medications and a listing of pain rescue medications will also be provided.

The listings will be sorted by DB treatment group, subject, chronological start date, primary system organ class/therapeutic class, preferred term/name and verbatim name.

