3 STATISTICAL METHODS

3.1 Statistical analysis strategy

The statistical analyses will be performed in accordance with the ICH E9 guideline and will be based on the pooled data from the individual study sites, unless otherwise stated.

Medpace will perform the statistical analysis of the efficacy, safety, and antibodies data.

Overall, the analysis strategy is to evaluate safety and efficacy of Dysport compared to Placebo after single administration (DB period), and to evaluate efficacy and safety over repeated Dysport treatments, using analyses by Active Treatment Cycle.

Listings will be presented by subject for DB and OL periods together while the tables associated with the DB period will be separated from the tables assessing repeat treatment with Dysport.

Only descriptive statistics of Stage 1 data will be provided.

Double-Blind Period (Stage 1 Cycle 1) Analyses

For the analysis of the DB period, tables will be displayed using the following treatment group (DB treatment group) labels, in the following order:

- Placebo: placebo groups from all cohorts will be pooled, including for mVPAQ pain, mVPAQ life interference and mFSFI pain domain of cohort 1 despite the change in recall period and time of assessments (see protocol version 3.0).
- Dysport
 - Groups by dose (Dysport 100U, 300U, 400U, 500U, etc.)
 - All Dysport

[figure not shown]
Note: Cohort 1 (100U), 2 (300U), 3 (400U) and 5 (500U) included PVD2 subjects only. Cohort 4 (400U) and 6 (500U) included PVD1 subjects only.

Repeat treatment: Active Treatment Analyses

To assess efficacy and safety data over repeat treatments, data will be analysed using the Active Treatment Cycle approach as described in [Figure 1](#) below. These analyses will be performed on the Active Treatment population:

- for subjects treated with Dysport in the DB period, the first cycle in the DB period will be the first Active Treatment Cycle.
- for subjects treated with placebo in the DB period, the first cycle in the OL period will be the first Active Treatment Cycle.

[Figure 1](#) Active Treatment Cycle Analysis

Three types of summary tables will be produced:

- Summary by number of active treatment cycles: these tables will present the long-term efficacy and safety data with all doses combined, and will display subjects with at least 1 (2, 3 and 4) active treatment cycles.
- Summary by dose received at each active treatment cycle: to evaluate the safety of each dose at a given cycle.

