- Description of the actual dose received in each cycle by DB treatment group and overall subjects from the safety population.
The number and percentage of subjects receiving the actual dose will be provided.
- Description of the actual dose at each active treatment cycle, by treatment received for the active treatment cycle and overall subjects from the safety population.
The number and percentage of subjects receiving the actual dose will be provided for each active cycle.
- A listing of exposure data will also be provided.

3.9.2 *Adverse events*

Adverse events will be coded using the Medical Dictionary for Regulatory Activities (MedDRA) latest version (23.0 or later) and presented by MedDRA preferred term and system organ class.

AEs will be classified as treatment-emergent AEs (TEAEs) according to the rules below:

- Events with start date (and time) on or after the date (and time) of first IMP administration.
- Events whose severity worsens on or after the date (and time) of first IMP administration.

A TEAE that occurs under a particular treatment cycle and worsens in intensity under a different treatment cycle will be considered as treatment emergent under the two treatment cycles. In the event of another occurrence of a TEAE with a change in intensity under a different treatment cycle, the subject will also be counted in that different treatment cycle. A given AE will be assigned to the dose received prior to the onset of the AE in the designated treatment cycle.

An overall summary table of all adverse events will be presented (as described in Section 3.9) and include the following:

- Subjects with any TEAEs,
- Subjects with any TEAEs by maximum intensity,
- Subjects with any TEAEs related to IMP,
- Subjects with any TEAEs related to IMP by maximum intensity,
- Subjects with any TEAEs leading to drug withdrawal,
- Subjects with any SAEs,

- Subjects with any TEAEs leading to death,
- Subjects with any SAEs related to IMP,
- Subjects with any TEAEs of special interest (AESIs).

This summary table will be also be provided by dose received at each active treatment cycle.

All TEAEs will be summarized with the number and percentage of subjects with adverse events classified by primary system organ class and preferred term. The number of occurrences of a TEAE will also be presented. This summary table will also be provided by dose received at each active treatment cycle.

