3.10.2 Missing or incomplete dates

In all listings, missing or incomplete dates should be left as they have been recorded. However, for calculation / sorting / assignation based on dates, the following methods will be used:

The most conservative approach will be systematically considered (i.e. if the onset date of an AE/concomitant medication is missing / incomplete, it is assumed to have occurred during the study treatment phase (i.e. a TEAE for AEs) except if the partial onset date or other data [stop date, ...] indicates differently).

- A missing/incomplete date of medical history or disease diagnosis will be assumed to have occurred before any study treatment,
- A medication with partial start and stop dates will be considered as concomitant treatment, except if the partial dates indicate differently,
- If an AE or SAE onset date is partial or missing, the event will be allocated to the first treatment where onset could have occurred (taking into account date and time stopped),
- If the start date of a medication is partial or missing, the medication will be assigned to the most recent treatment received on or before the medication start date (taking into account date stopped).

Where this is possible, the derivations based on a partial date will be presented as superior inequalities (i.e.: for an AE started in FEB2004 after the administration performed on 31JAN2004, the days since last dose will be “ ≥ 2 ”, similarly the duration of ongoing AEs or medication will be “ $\geq xx$ ” according to the start and last visit dates).

If the date of diagnosis for provoked vestibulodynia is partial, the duration of provoked vestibulodynia will be calculated as follow: 1) If only day is missing, only month and year will be used in calculation. 2) If month is missing, only year will be used in calculation. 3) No imputation should be done at the data level.

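### The SAP's by-cycle concomitant treatment rule counts only treatments in use on the injection day, so fully dated treatments started later are left out of the cycle in which they began

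*SAP*

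**What the plan says.** SAP 3.6 classifies treatments at two levels.

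- **Study level.** Treatments are prior (P), prior and concomitant (PC) or concomitant (C), relative to the first IMP administration. Category C is defined by "Start date on or after the date of first IMP administration", with no upper limit, and the concomitant tables use C and PC.
- **Cycle level.** "A treatment will be considered concomitant to a cycle if the start date was on or before the IMP administration for the cycle", with the further condition that "the stop date was on or after the IMP administration for the cycle". The SAP adds: "A treatment can be concomitant under more than one treatment cycle, but it will be considered as concomitant only once in the overall period".

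The cycle rule feeds a defined set of tables. Those on concomitant medications, therapies and "surgical procedures will be presented during Active Treatment period all doses combined by Active Treatment Cycle and overall", for the Active Treatment population. SAP 3.1 numbers the cycles: "for subjects treated with placebo in the DB period, the first cycle in the OL period will be the first Active Treatment Cycle".

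Two other rules in the SAP assign records to cycles. Under SAP 3.10.2, if a medication's start date is partial or missing, "the medication will be assigned to the most recent treatment received on or before the medication start date". For adverse events, SAP 3.9.2 says: "A given AE will be assigned to the dose received prior to the onset of the AE in the designated treatment cycle".

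**The concern.** A table of concomitant treatments by cycle should show what subjects used during each Dysport cycle. A rule that requires the treatment to span the injection date shows what they were using on one day of it. Treatments begun after the injection, including any given for an adverse event, are the ones most informative about the cycle, and they are the ones dropped.

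The protocol collects these data deliberately. New or changed medications and non-drug therapies are recorded at the Week 2 call and at the Week 6, Week 12 and additional visits of each cycle (Protocol 5.2.2 and 5.2.3). Protocol 6.3 foresees sex therapy being started after the initial restricted period. Evaluation of concomitant medication and therapy use is a listed safety endpoint (Protocol 3.2.3), safety is the primary objective of Stage 1, and SAP 3.1 evaluates safety over repeated treatment by Active Treatment Cycle.

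As written, the cycle columns would not reconcile with an overall column built from C and PC. Nor could they be read by cycle alongside the adverse event tables.

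**Working it through.** The plan gives no figure to reproduce, so the check applies the written rule to dated examples and then counts start days.

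**Inputs**
- SAP rule (SAP 3.6): counted in cycle *i* if start ≤ injection *i* ≤ stop.
- Minimum spacing between injections: 12 weeks = 84 days (Protocol 3.7.3).
- At most four cycles (Protocol 3.8). At minimum spacing, injections fall on Days 1, 85, 169 and 253. The end-of-study visit is Day 337 (Protocol Table 3).
- Comparison rule (overlap): start before injection *i*+1, or by end of study in the last cycle, and stop on or after injection *i*.

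**Examples**

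| Treatment | SAP rule | Overlap rule |
|---|---|---|
| Day 1 to Day 5 | cycle 1 | cycle 1 |
| Day 10 to Day 20 | none | cycle 1 |
| Day 30 to Day 100 | cycle 2 only | cycles 1 and 2 |
| One-day procedure, Day 40 | none | cycle 1 |
| Day 260, ongoing | none | cycle 4 |

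All five are category C at study level. Same-day starts are handled correctly.

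**Start-day count, non-last cycle** (84 possible start days, Day 1 to Day 84, next injection Day 85; course of *L* days, so stop = start + *L* − 1)
- Counted in own cycle: start on Day 1 only, so 1 of 84 (1.2%).
- Counted only from the next cycle: start after Day 1 and start + *L* − 1 ≥ 85, which gives *L* − 1 start days (for *L* ≤ 84).
- Counted in no cycle: 84 − 1 − (*L* − 1) = 84 − *L*.

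| Length | Own cycle | Later cycle only | No cycle |
|---|---|---|---|
| 1 day | 1 | 0 | 83/84 (98.8%) |
| 7 days | 1 | 6 | 77/84 (91.7%) |
| 14 days | 1 | 13 | 70/84 (83.3%) |
| 28 days | 1 | 27 | 56/84 (66.7%) |
| 84 days | 1 | 83 | 0/84 |

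**Last cycle.** There is no later injection, so 83 of 84 start days (98.8%) are counted nowhere, whatever the length.

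Leaving out the injection day changes the denominator to 83 and gives 77/83 (92.8%), 70/83 (84.3%) and 56/83 (67.5%) for 7, 14 and 28 days. The conclusion is the same. Under the overlap rule, all 84 start days are counted in their own cycle in every case.

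**Against the other SAP rules.** An adverse event on Day 10 is assigned to cycle 1 (SAP 3.9.2). A drug given for it on Days 10 to 20, fully dated, is assigned to no cycle. If that drug's start date were incomplete, SAP 3.10.2 would place it by the last injection on or before the start. The less complete record is then counted where the complete one is not.

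**The case against.** The strongest reply is that the sentence says *if*, not *only if*. Categories C and PC define concomitance just above it, and SAP 3.10.2 suggests that cycle of start was intended, so the cycle rule may be meant only for carry-over into later cycles. That may be the intention. But the SAP writes no other per-cycle criterion for complete dates, and a programmer following it would produce the omission.

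Other points stand in part.
- The SAP 3.10.2 bullet covers medications only, not procedures or non-drug therapies, so the clash with that rule is limited to medications.
- No planned table joins treatments and adverse events by cycle; the mismatch arises when the two sets are read together.
- The percentages describe how the rule behaves under assumed start days and course lengths, for new starts only. They do not estimate the share of all treatments lost. Protocol 6.3 favours stable background therapy, which is counted correctly when in use at injection.
- Rescue medication for intercourse and dilator insertion has its own summaries by number of active cycles (SAP 3.8.2), and SAP 3.6 lists rescue and prohibited medications separately.
- Stage 2 was cancelled. The analysis is descriptive, on cohorts planned at 58 evaluable subjects (five of 10 and one of 8).

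These points limit the consequence; they do not make the rule right.

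**Conclusion.** The concern holds: the rule is wrong as written, not merely short of detail. In the by-Active-Treatment-Cycle columns, a fully dated treatment started after injection day is always missing from its own cycle. It is missing from every cycle unless it is still in use at a later injection. A one-day entry, such as a surgical procedure, is counted only if it falls on an injection day.

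The size figures rest on 84-day spacing and evenly spread starts; longer spacing raises the non-last-cycle shares. The documents do not allow the number of affected treatments to be estimated.

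The effect is confined to the cycle columns of descriptive tables. The double-blind period tables, which use C and PC, and the listings appear unaffected, and no test or estimate depends on the rule. It should be corrected because it misstates a listed safety evaluation and the correction is simple.

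**What to change.** In SAP 3.6, replace the cycle rule with an overlap definition. A treatment is concomitant to Active Treatment Cycle *i* if it starts before injection *i*+1 (or on or before the end of study for the last cycle) and either stops on or after injection *i* or is ongoing.

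Cross-refer to the numbering in SAP 3.1, so that for subjects given placebo first, cycle 1 begins at the first open-label injection. The numbering is already defined there; the cross-reference only ties the rule to it.

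Edit SAP 3.10.2 so that complete and partial dates follow the same rule, and state that it also covers non-drug therapies and procedures.

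The cost is one sentence in SAP 3.6, the cross-reference, the matching edit in 3.10.2 and one changed derivation for the by-cycle concomitant tables. No new data are needed.

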3.7 Subject compliance

A listing will be presented for drug administration (volume administered, specified difficulties during drug administration, injection sites, date) at all treatment cycles by DB treatment group and subject.

3.8 Efficacy analysis

The efficacy endpoints will be summarized using the analysis strategy in Section 3.1. Descriptive statistics will be provided for:

- the DB period, by DB treatment group for the mITT population.
- the Active Treatment Cycle, on the Active Treatment population: by number of active treatment cycles (all doses combined and/or by dose). The mITT population will be the primary population for analysis of efficacy data. Week 6 and Week 12 will be the timepoints of primary interest.

3.8.1 Primary efficacy analysis

Not applicable as the primary objective of Stage 1 is related to safety.

3.8.2 Secondary efficacy analyses

Vestibular pain using a vaginal dilator

A set of 8 vaginal dilators of increasing diameter (#1 being the smallest and #8 being the largest) will be used to provoke pain to allow assessment of the vestibular pain intensity in each subject. Subjects will be required to rate the pain for each dilator size on an 11-point NRS at each visit. Pain score will be entered by the investigator (or delegated site staff) in the eCRF.

Based on the subjective pain threshold, the largest sized dilator that the subject accepts to test, will be defined as the Dilator Maximum Tested Size (DMTS) that will be established at the Baseline Visit. The dilator test will be used to assess the change from Baseline in the vaginal dilator induced pain as reported on an NRS (using the DMTS reported at baseline) as well as the dilator size that provokes maximum pain. If a dilator size is not tested due to pain intensity, the pain will be scored at 10. If the test is not done due to other reasons, then the pain score will be considered as missing. Endpoints and corresponding analyses are described in [Table 1](#).

Table 1 Dilator Induced Pain - Endpoints and Corresponding Analyses

Endpoint	Analyses
Mean change from Baseline to each post-treatment visit in the vaginal dilator induced pain as reported on the 11-point NRS[1]	
Convention:
 
According to the mITT Population definition, there will be no missing data for Week 6. For Week 12, the missing values will be kept as missing.
 
- descriptive statistics: actual values and change from baseline values will be presented at all timepoints (over the double-blind and open-label periods). A plot of mean changes over time from baseline in pain scores will be provided by treatment group for DB period.
 
Active Treatment Cycle:
 
 - A summary by number of active treatment cycles. - A plot of mean changes over time from baseline in pain scores will be provided by randomized treatment group for Week 6 and Week 12 over both of the DB and first OL period.
Proportion of subjects who reported at least a 50% decrease in vaginal dilator induced pain as reported on the 11-point NRS[1] at each post-treatment	
Convention:
 
According to the mITT Population definition, there will be no missing data for Week 6. For Week 12, the missing values will be kept as missing.
 
- descriptive statistics will be presented at all timepoints.

visit (repeat for 30% decrease)	Active Treatment Cycle: - A summary by number of active treatment cycles will be used.
Proportion of subjects who reported at least 2-point decrease from baseline in vaginal dilator pain as reported on the 11-point NRS[1] at each post-treatment visit	
 - descriptive statistics: actual values and change from baseline values will be presented at all timepoints. - Number and percentage of each size will be provided at all timepoints. 
Active Treatment Cycle:
 
 - A summary by number of active treatment cycles will be used.
Mean change from Baseline to each post-treatment visit in the dilator size that provokes maximum tolerated pain	
Composite score derivation:
 
The composite score for the vaginal dilator induced pain and dilator size is the sum of all pain measurements across the full range of dilator sizes. In the construction of this endpoint, the pain score will be 10 for any dilator size that is beyond the DTMS. As described in section 3.10.1, there should be at least 6 pain scores (recorded by the investigator) to calculate the composite score. When there is a dilator size score missing, pain score will be imputed by the average of the previous (smaller dilator size) and the following (larger dilator size) valid values. For example, if the pain score for dilator size 4 is missing, then it will be imputed by the average of the pain scores for dilator size 3 and size 5 when both of them are available.
 
 - descriptive statistics: actual values and change from baseline values will be presented at all timepoints. 
Active Treatment Cycle:
 
 - A summary by number of active treatment cycles will be used.

[1] Using DTMS at baseline.

Pain during insertion of vaginal dilator number 6 size

Cohort 1: once a week during the Screening period (Day -14 to Day 1), and once a week during the month (28 days) prior to the next planned visit, all subjects are to rate pain following insertion of the number 6 vaginal dilator (11-point NRS) and to record details of associated pain medication if consumed. Data are recorded in the patient's eDiary.

Cohort 2 onwards: once a week during the 2 weeks preceding the next planned visit, all subjects are to rate pain following insertion of the number 6 vaginal dilator (11-point NRS) and to record details of associated pain medication if consumed. Data are recorded in the patient's eDiary.

Endpoints and corresponding analyses are described in [Table 2](#).

Table 2 Dilator #6 - Endpoints and Corresponding Analyses

Endpoint	Analyses
Mean change from Baseline to each post-treatment visit in pain during insertion of vaginal dilator number 6 size as reported on the 11-point NRS	
Convention:
 
Average of the values over the last 2 weeks preceding the visit. The average will be missing if and only if the two pain scores are both missing. This rule will be applicable for all cohorts including cohort 1.
 
- descriptive statistics: actual values and change from baseline values will be presented at all timepoints.
 
Active Treatment Cycle:
 
- A summary by number of active treatment cycles will be used.

Proportion of subjects who reported at least a 50% decrease in pain during insertion of vaginal dilator number 6 size as reported on the 11-point NRS at each post-treatment visit (repeat for 30% decrease)	
Convention:
 
Average of the values over the last 2 weeks preceding the visit. The average will be missing if and only if the two pain scores are both missing. This rule will be applicable for all cohorts including cohort 1.
 
- descriptive statistics will be presented at all timepoints.
 
Active Treatment Cycle:
 
- A summary by number of active treatment cycles will be used.

Proportion of subjects who reported at least 2-point decrease from baseline at each post-treatment visit	
- descriptive statistics: number and percentage of subjects using pain rescue medication within the 2 weeks period preceding each visit, in subjects with non-missing pain score value in the corresponding period.

vaginal dilator number 6 size.	
Active Treatment Cycle: - A summary by number of active treatment cycles will be used.
 
Subjects having taken pain rescue medication associated with insertion of vaginal dilator will be listed, along with period, medication (primary system organ class, preferred term and verbatim text), name, number of pills, dosage of each pill, route, date, taken before/after the dilator insertion and pain during the dilator insertion in the corresponding week.

--------------------------------	--

Frequency of intercourse and pain during intercourse

Cohort 1: Each day during the Screening period (Day -14 to Day 1), and during the month (28 days) preceding the next planned visit, subjects are to record in the eDiary if they had intercourse, the number of intercourse instances, corresponding pain during each intercourse instance (using an 11-point NRS) and details of pain rescue medication, if taken, to prevent or treat vestibular pain.

Cohort 2 onwards: Each day during the Screening period and during the 2-week period preceding the next planned visit, subjects are to record if they had intercourse, the number of intercourse instances, corresponding pain during each intercourse instance on an 11-point NRS and details of pain rescue medication, if taken, to prevent or treat vestibular pain.

Intercourse diary entry with no intercourse in the previous 24 hours and pain score entered as 0 will be considered as no intercourse in the previous 24 hours. Entry with no intercourse in the previous 24 hours and pain score different from 0 will be considered as an intercourse entry with the entered pain score.

Endpoints and corresponding analyses are described in [Table 3](#).

Table 3 Intercourse - Endpoints and Corresponding Analyses

Endpoint	Analyses
Mean change from baseline to each post-treatment visit in the pain during intercourse as reported on the 11-point NRS	
Conventions: Analysis of pain will be done on the subjects who had intercourse in the corresponding period.
 
Average pain score over the week preceding the visit: The weekly average will be calculated as the average of the score over the last week (7 days) prior to the visit, for all cohorts (including cohort 1). The weekly average will be calculated if at least 1 pain score has been recorded over the considered week.
 
Average pain score over the 2 weeks preceding the visit: The 2-week average will be calculated as the average of the score over the last 2 weeks (14 days) prior to the visit, for all cohorts (including cohort 1). The 2-week average will be calculated if at least 1 pain score has been recorded in the considered 2-week period.

	
 - descriptive statistics: actual values and change from baseline values will be presented at all timepoints. In the same table, number of subjects with or without partner at each timepoint will be also presented. 
Active Treatment Cycle:
 
 - A summary by number of active treatment cycles will be used.
Mean change from baseline to each post-treatment visit in the number of intercourse instances in subjects with partners	
Conventions:
 
Analysis will be done on the subjects who have a partner at baseline and at the specific visit (DB Week 6, or Week 12).
 
Number of intercourse instances over the week preceding the visit
 
The number of intercourse instances over the week preceding the visit will be calculated as the total number of intercourse instances over 7 days prior to the visit. There should be at least 1 eDiary input recorded in the week for calculating the number of intercourse instances over the period, otherwise it will be considered missing.
 
Number of intercourse instances over the 2 weeks preceding the visit
 
The number of intercourse instances over the 2 weeks preceding the visit will be calculated as the total recorded number of intercourse instances over 14 days prior to the visit. There should be at least 1 eDiary input recorded in the period for calculating the number of intercourse instances over the period, otherwise it will be considered missing.
 
 - descriptive statistics: actual values and change from baseline values will be presented at all timepoints. 
Active treatment cycle:
 
 - A summary by number of active treatment cycles will be used.
Proportion of subjects having taken pain rescue medication associated with intercourse	
 - descriptive statistics: number and percentage of subjects using pain rescue medication within the 1-week/2-week period preceding each visit, in subjects with non-missing pain score value in the corresponding period. 
Active Treatment Cycle:
 
 - A summary by number of active treatment cycles will be used.

	Subjects having taken pain rescue medication associated with intercourse will be listed, along with period, medication (primary system organ class, preferred term and verbatim text), name, number of pills, dosage of each pill, route, date, taken before/after the intercourse instance and pain during the intercourse in the corresponding week.
--	--

3.8.3 *Exploratory efficacy analyses*

Clinical Global Impression (CGI) and Patient Global Impression (PGI)

Endpoints and corresponding analyses are described in **Error! Reference source not found..**

CGI was assessed by the investigator using a 7-point Likert scale during the visit. PGI-S and PGI-C: Subjects were to assess PGI-S and PGI-C in the eDiary one week prior to the next planned visit and at the visit. The outcome for the visit will be calculated as the average of a) the average of the entries on the date of the visit (in case of several entries on the day of the visit) and b) the average of the entries within the week prior to the visit (in case of several entries).

Table 4 CGI and PGI - Endpoints and Corresponding Analyses

Endpoint	Analyses
Mean score of CGI	
 - descriptive statistics will be presented at all timepoints. Active treatment cycle: 
 - A summary by number of active treatment cycles will be used.
Mean change from baseline to each post-treatment visit in the PGI-S	
 - descriptive statistics: actual values and change from baseline values will be presented at all timepoints. Active treatment cycle: 
 - A summary by number of active treatment cycles will be used.
Mean PGI-C at each post-treatment visit	
 - descriptive statistics will be presented at all timepoints. Active treatment cycle: 
 - A summary by number of active treatment cycles will be used.

mVPAQ and mFSFI

Endpoints and corresponding analyses are described in [Table 5](#).

mVPAQ questionnaire is provided in protocol Appendix 1. It contains 6 subscales: pain severity, emotional response, cognitive response, life interference, sexual

function interference, self-stimulation/penetration interference. The subscale score is the average of the item scores under the subscale.

For mVPAQ, the analysis of life interference subscale will be done with and without the item 'ability to fall asleep'. The analysis of pain severity subscale will be done with and without the items 'unpleasantness' and 'distress'. All these items will be included/excluded together when calculating subscale score.

For mVPAQ pain subscale, life interference subscale and mFSFI pain domain: Subjects were to record in the e-diary the data related to the completion of these questionnaires in the eDiary one week prior to the next planned visit and at the visit. The subscale scores for the visit will be calculated as the average of a) the average of the subscale scores entered on the date of the visit and b) the average of the subscale scores entered within the week prior to the visit. For other mVPAQ subscales and mFSFI domains, data were recorded by the subject at the site during the visit.

Table 5 mVPAQ and mFSFI - Endpoints and Corresponding Analyses

Scales	Endpoints	Analyses/ Conventions
Modified Vulvar Pain Assessment Questionnaire (mVPAQ) – Pain severity subscale	Change from baseline in each question and subscale score	The score for each question ranges from 0 to 4 and a mean score is computed. - descriptive statistics: actual values and change from baseline values will be presented at all timepoints.
Modified Vulvar Pain Assessment Questionnaire (mVPAQ) – Life interference subscale	Change from baseline in each question and subscale score	The score for each question ranges from 0 to 4 and a mean score is computed. - descriptive statistics: actual values and change from baseline values will be presented at all timepoints.
Modified Vulvar Pain Assessment Questionnaire (mVPAQ) – other subscales	Change from baseline in each subscale score	The score for each question ranges from 0 to 4 and a mean score is computed. - descriptive statistics: actual values and change from baseline values will be presented at all timepoints.
modified Female Sexual Function Index (mFSFI) – pain domain	Change from baseline in each question and total score	See Table 6 for domain and total score calculation. - descriptive statistics: actual values and change from baseline values will be presented at all timepoints.
Modified Female Sexual Function Index (mFSFI) – other domains	Change from baseline total score in each domain	See Table 6 for domain and total score calculation. - descriptive statistics: actual values and change from baseline values will be presented at all timepoints.

modified Female Sexual Function Index (mFSFI) – all domains	Change from baseline in mFSFI total score.	See Table 6 for domain and total score calculation. - descriptive statistics: actual values and change from baseline values will be presented at all timepoints.
Pelvic floor muscles pressure – Resting and Squeezing	Mean change from baseline in the pelvic floor muscles pressure for the 2 conditions: - Resting vaginal pressure - Maximal 'squeeze' pressure, and the difference between the 2 conditions (squeeze minus rest condition)	Conventions: The mean of the 3 measurements will be used. The mean will be missing if and only if the 3 measurements are missing. An assessment will be invalidated if the measurement is not accurate as specified by the investigator or if subject had a vaginal delivery. Difference of the mean between Squeeze and rest conditions will be calculated. - descriptive statistics: actual values and change from baseline values will be presented at all timepoints.
Patient Health Questionnaire (PHQ-9)	Change from baseline in the PHQ-9 total score	See Appendix 3 from protocol for total score definition. PHQ-9 questionnaire comprises 9 items, each of which is scored 0 to 3, providing a 0 to 27 total score. (If several entries are available on the date of visit, the average of the total score will be used) - descriptive statistics: actual values and change from baseline values will be presented at all timepoints.
36-Item Short Form Health Survey (SF-36)	Change from baseline in all 8 domains scores, and the 2 components (physical and mental)	The eight dimensions of SF-36 and the Physical and Mental component will be derived by OPTUM. - descriptive statistics: actual values and change from baseline values will be presented at all timepoints.

Table 6. mFSFI Score Calculation

Domain	Questions	Score Range	Factor	Minimum Score	Maximum Score
Desire	1, 2	1 – 5	0.6	1.2	6.0
Arousal	3, 4, 5, 6	0 – 5	0.3	0	6.0
Lubrication	7, 8, 9, 10	0 – 5	0.3	0	6.0
Orgasm	11, 12, 13	0 – 5	0.4	0	6.0
Satisfaction	14, 15, 16	0 (or 1) – 5	0.4	0.8	6.0
Pain	17, 18, 19	0 – 5	0.4	0	6.0
Full Scale Score Range				2.0	36.0

Note: The individual domain scores and full scale (overall) score of the FSFI can be derived from the computational formula outlined in the table above (Rosen etc 2000). For individual domain scores, add the scores of the individual items that comprise the domain and multiply the sum by the domain factor. Add the six domain scores to obtain the full-scale score. It should be noted that within the individual domains, a domain score of zero indicates that the subject reported having no sexual activity during the recall period.

